enroll	Patients who are enrolled in the trial are those who have been assigned to a treatment and have received at least 1 dose of study treatment.
enter	Patients who are entered in the trial are those who have signed the informed consent form directly or through their legally acceptable representatives.
ERB/IRB	ethical review board/institutional review board: /A board or committee (institutional, regional, or national) composed of medical and nonmedical members whose responsibility is to verify that the safety, welfare, and human rights of the patients participating in a clinical study are protected.
GCP	good clinical practice
G-CSF	granulocyte colony stimulating factor
GIST	gastrointestinal stromal tumors
HR	hazard ratio
IB	Investigator's Brochure
ICF	informed consent form
ICH	International Conference on Harmonisation
IG	immunogenicity
IgG1	immunoglobulin G, subclass 1
IHC	immunohistochemistry
informed consent	A process by which a patient voluntarily confirms his or her willingness to participate in a particular trial, after having been informed of all aspects of the trial that are relevant to the patient's decision to participate. Informed consent is documented by means of a written, signed and dated informed consent form.
interim analysis	An analysis of clinical study data that is conducted before the final reporting database is authorized for datalock.
IRR	infusion-related reaction

investigational product (IP)	A pharmaceutical form of an active substance or placebo being tested or used as a reference in a clinical trial. Investigational product includes a product with a marketing authorization when: 
 1. used or assembled (formulated or packaged) in a way different from the authorized form 2. used for an unauthorized indication or 3. used to gain further information about the authorized form
investigator	A person responsible for the conduct of the clinical study at a study site. If a study is conducted by a team of individuals at a study site, the investigator is the responsible leader of the team and may be called the principal investigator.
ITT	intent-to-treat
IV	intravenous(ly)
IWRS	Interactive Web Response System
legal representative	An individual, judicial, or other body authorized under applicable law to consent on behalf of a prospective patient, to the patient's participation in the clinical study.

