7.3. Method of Assignment to Treatment

Patients who meet all criteria for enrollment will be assigned to receive treatment. After the patient signs the ICF, the site will register the patient in the Interactive Web Response System (IWRS), which is web-based and accessible 24 hours a day. The IWRS registration consists of assigning the patient a unique study identification number. Once the patient is registered through the IWRS, he/she is considered to be enrolled in the study.

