8.4. Procedure/Sampling Compliance

Every attempt will be made to enroll patients who have the ability to understand and comply with instructions. Noncompliant patients may be discontinued from the study.

The collection times of safety assessments, PK samples, and efficacy measurements are given as targets to be achieved within reasonable limits. The scheduled time points may be subject to minor alterations; however, the actual collection time must be correctly recorded on the eCRF.

The scheduled collection times may be modified by the sponsor based on analysis of the safety and PK information obtained during the study. Any major modifications that might affect the conduct of the study, patient safety, and/or data integrity will be detailed in a protocol amendment.

9. Data Management Methods

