10.6. Efficacy

The following secondary efficacy endpoints will be measured:

Progression-free survival (PFS): is defined as the time from enrollment until the first radiographic documentation of objective progression as defined by RECIST (v1.1) ([Attachment 8](#)), or death from any cause. Patients who die without a reported prior progression will be considered to have progressed on the day of their death. Patients who did not progress or who are lost to follow-up will be censored at the day of their last radiographic tumor assessment. If no baseline or postbaseline radiologic assessment is available, the patient will be censored at the date of enrollment. If death or PD occurs after 2 or more consecutive missing radiographic visits, censoring will occur at the date of the last radiographic visit prior to the missed visits. The use of a new anticancer therapy or the performance of a surgical resection prior to the occurrence of PD will result in censoring at the date of last radiographic assessment prior to initiation of new therapy or surgical resection.

3-month PFS: estimated as the total number of patients who did not progress 3 months after enrollment divided by the total number of patients.

Overall response rate (ORR): estimated as the total number of CRs, complete responses unconfirmed (CRus), and PRs divided by the total number of patients.

Disease control rate (DCR): is computed as the total number of patients with the best overall response of CR, CRu, PR, or SD divided by the total number of patients.

Rate of Resectability: is defined as the total number of patients who are resectable (see definition of resectability in Section 4) divided by the total number of patients.

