Attachment 1. Protocol JGDM Study Schedule

Perform procedures as indicated in the following tables for the baseline, treatment, and posttreatment periods, respectively.

All screening/baseline evaluations are performed within 14 days prior to enrollment, unless otherwise specified. Patients who meet all criteria for enrollment will be assigned to receive treatment. After the patient signs the informed consent form, the site will register the patient in the Interactive Web Response System, which is web-based and accessible 24 hours a day.

Baseline Schedule of Activities

Procedure Category	Protocol Sections	Procedure	Study Period		Comments
			Baseline		
			Cycle	BL	
			Visit	0	
			Duration	Up to 14 days (except where noted)	
Relative Day from Enrollment	≤14	≤7			
Study Entry/ Enrollment	11.1	Informed Consent	X (within 28 days of enrollment)		Written informed consent must be obtained prior to any study-specific screening evaluations. For screening purposes, required assessments performed prior to the date of consent may be used provided they are noted exceptions.
	6.1 7.2.3.1.2.4	Inclusion/Exclusion Evaluation and IWRS		X	Patients who meet all criteria for enrollment will be assigned to receive treatment. After the patient signs the ICF, the site will register the patient in the IWRS. After enrollment, patients should receive their first dose of treatment within 72 hours (3 days) whenever possible.
Medical History	8.1.2	Medical History	X		Any preexisting and pretreatment toxicity (treatment- or disease-related) should be documented and recorded as part of the pretreatment medical history. Disease characteristics at initial diagnosis and at study entry will be collected. All adverse events must be recorded after signing the informed consent.
	6.1	Demography	X		Year of birth, sex, and race/ethnicity will be collected at baseline.
	6.1	Prior Treatment Therapies of Underlying Disease	X		Prior treatment includes any treatment for underlying disease, including maintenance therapy. Start and stop dates should be documented as well.
Physical Examination	6.1	Physical Examination		X	Physical examination at baseline includes height, weight, and BSA measurement.
	6.1 Attachment 6	ECOG Performance Status		X	Refer to Attachment 6 for details.
	6.1	Vital Signs		X	Vital signs include blood pressure, pulse, and temperature.

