	8.1.3.1	ECG	X			X				Twelve-lead ECGs are to be collected on Day 1 of monotherapy Cycle 1 and on Day 1 of combination therapy Cycles 2-7. Patients who stop doxorubicin prior to Cycle 7 will undergo the same cardiac monitoring assessment. ECGs will be read locally and measurements will be electronically submitted to a central vendor.	
	8.1.3.2	Echocardiogram or MUGA							X	Echocardiograms or MUGA scans must be performed at the end of combination therapy Cycles 5 and 7 and when clinically indicated. After Cycle 7, (resting LVEF ≥50%), perform echocardiograms or MUGA at the 30-day follow-up visit. Patients who stop doxorubicin prior to Cycle 7 will undergo the same cardiac monitoring assessment. For patients with LVEF <50% or other cardiac dysfunction, perform more frequently, if clinically indicated.	
	8.2.3.3	PET Scan				X				Mandatory PET scan must be collected up to 3 days prior to the first dose of C2D1. PET scans will be read locally by the investigator and sent to a central vendor where the images will be stored.	

Procedure Category	Protocol Section	Procedure	Treatment Period				Comments	
			Study Period		Treatment Period			
					Olaratumab Monotherapy	Combination Therapy Olaratumab + Doxorubicin		
			Cycle (21-day cycle ±3 days)		1			2-7
Relative Day within Cycle (± 3 days)		1 ^{ab}	8 ^a	1 ^a	8 ^{ab}			
Efficacy Assessment	Attachment 8	Imaging Studies (CT/MRI) Tumor Assessments (according to RECIST v1.1)			X		Imaging studies and tumor assessments are to be obtained every 6 weeks (up to 7 days before), irrespective of treatment cycles as calculated from enrollment, until documented progression for patients with CR, PR, or SD, and/or for patients who have discontinued study treatment due to toxicity or reasons other than PD. Refer to Attachment 8 for details. CT/MRI scans will be read locally and a scan will also be sent for storage at a central vendor.	
Adverse Events Collection/CTCAE Grading	8.1.2	Toxicity Assessment	X	X	X	X	All AEs considered at least possibly related to study treatment will be followed until resolution, stabilization, or return to baseline, or until deemed irreversible.	
Concomitant Therapy	7.5	Concomitant Medications	X	X	X	X	Concomitant medications will be recorded throughout the treatment period, including those taken during the 30 days after the last dose of all study treatment.	

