The main goal of confirmation of objective response in clinical trials is to avoid overestimating the response rate observed. The confirmation of response is particularly important in *nonrandomized trials* where response (CR/PR) is the primary end point. In this setting, to be assigned a status of PR/CR, changes in tumor measurements must be confirmed by repeat assessments that should be performed no less than 4 weeks after the criteria for response are first met. To confirm a response of CR, a full assessment of all target and nontarget lesions that were present at baseline must occur, including those measured by bone scan. To confirm a PR or SD, a full assessment of target lesions that were present at baseline must occur; assessment of nontargets is not required.

However, in *randomized trial* (Phase 2 or 3) or studies where SD or progression is the primary endpoints, confirmation of response is not required. But, elimination of the requirement may increase the importance of central review to protect against bias, in particular of studies which are not blinded.

In the case of SD, follow-up measurements must have met the SD criteria at least once after start of treatment at a minimum interval not less than 6 weeks measured from first dose.

Duration of Overall Response

The duration of overall response is measured from the time measurement criteria are first met for CR or PR (whichever is first recorded) until the first date that disease is recurrent or objective progression is observed (taking as reference for PD the smallest measurements recorded on study).

The duration of overall CR is measured from the time measurement criteria are first met for CR until the first date that recurrent disease is objectively documented.

Duration of Stable Disease

Stable disease is measured from the start of the treatment (in randomized trials, from date of randomization) until the criteria for objective progression are met, taking as reference the smallest sum on study (if the baseline sum is the smallest, that is the reference for calculation of PD).

Independent Review of Response and Progression

When objective response (CR + PR) is the primary end point, and when key drug development decisions are based on the observation of a minimum number of responders, it is recommended that all claimed responses be reviewed by an expert(s) independent of the study. If the study is a randomized trial, ideally reviewers should be blinded to treatment assignment.

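### The 6-week minimum for stable disease does not fit the first on-treatment scan window, so disease control rate may be understated for patients whose only disease control is stable disease at that scan

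*Protocol*

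**What the plan says.** **SD rule.** Protocol Attachment 8, under confirmation of response, credits SD only if its criteria hold on one or more follow-up assessments "at a minimum interval not less than 6 weeks measured from first dose". The same attachment derives best overall response by algorithm from the investigator's assessments, subject to any confirmation requirement.

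**Scan timing.** The on-treatment table in Attachment 1 asks for tumor imaging "every 6 weeks (up to 7 days before), irrespective of treatment cycles as calculated from enrollment". The allowance is on the early side only.

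**First dose.** The baseline table in Attachment 1 says: "After enrollment, patients should receive their first dose of treatment within 72 hours (3 days) whenever possible".

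**Enrollment.** There are two definitions. Protocol Section 4 treats enrolled patients as those "assigned to a treatment and have received at least 1 dose of study treatment". Section 7.3 says: "Once the patient is registered through the IWRS, he/she is considered to be enrolled in the study".

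**Endpoint.** Protocol Section 10.6 defines DCR as the "total number of patients with the best overall response of CR, CRu, PR, or SD divided by the total number of patients". SAP Sections 5.3.5 and 5.10 give the same components. Neither document's DCR text repeats a minimum interval for SD or says how an earlier SD is to be classified.

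**After resection.** Under Protocol Section 6.2, resection ends study treatment, and resected patients have no further imaging for progression.

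**The concern.** The two rules start from different dates and meet at the wrong end. The SD clock starts at first dose and opens at 6 weeks. The scan clock starts at enrollment, which is no later than first dose, and its first window closes at 6 weeks. A site that keeps exactly to the schedule will therefore usually produce a first scan that is too early to support SD.

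This matters for patients with no second chance to qualify. A patient who is stable at the first scan and then progresses by the second, dies, is resected, starts other therapy or drops out has no later scan on which SD can be met. That patient stays in the DCR denominator but not in the numerator. The trial enrolls potentially resectable disease, so early resection after a stable scan is a plausible and welcome course, yet it could be scored as no disease control.

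**Working it through.** The documents give no planned DCR and no expected number of patients with SD, so there is no figure of the plan's own to reproduce on this point. The check is date arithmetic.

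**Inputs**
- SD minimum: 6 × 7 = 42 days from first dose (Attachment 8).
- First scan: days 42 − 7 = 35 to 42 after enrollment (Attachment 1).
- Second scan: days 84 − 7 = 77 to 84 after enrollment (Attachment 1).
- Lag from enrollment to first dose: 0 to 3 days (Attachment 1; a target, so it can be longer).
- Day count: plain difference, or end − start + 1 as in SAP Section 5.3.

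**First scan, days since first dose = scan day − lag**

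| Lag (days) | Interval (days) | Scan days reaching 42, plain difference | Scan days reaching 42, SAP +1 count |
|---|---|---|---|
| 0 | 35–42 | 1 of 8 | 2 of 8 |
| 1 | 34–41 | 0 of 8 | 1 of 8 |
| 2 | 33–40 | 0 of 8 | 0 of 8 |
| 3 | 32–39 | 0 of 8 | 0 of 8 |
| All | 32–42 | 1 of 32 | 3 of 32 |

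A lag above 3 days moves every interval further below 42. If enrollment is read as requiring a dose (Section 4), the lag can be taken as 0 and only the top row applies. For comparison, a symmetric window of days 35 to 49 would let 26 of 60 day-lag pairs qualify by plain difference, so the early-only allowance drives much of the misfit.

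**Second scan.** Shortest interval 77 − 3 = 74 days, longest 84 − 0 = 84 days. It always meets the minimum.

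**Effect per patient.** With the planned 35 patients, each stable patient who fails to qualify lowers DCR by 1/35 = 2.9 points. The step is slightly smaller if replacement of nonevaluable patients takes enrollment above 35.

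**How many patients (assumption, for scale only).** Suppose PFS is exponential, S(t) = exp(−ln 2 × t/median), with the medians that Protocol Section 5.1 quotes from the earlier Phase 2 study in advanced disease.
- Median 6.6 months: S(6 weeks) − S(12 weeks) = 0.865 − 0.748 = 0.117; × 35 = 4.1 patients.
- Median 4.1 months: 0.792 − 0.627 = 0.165; × 35 = 5.8 patients.

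Under that assumption about 4 to 6 patients progress or die between weeks 6 and 12. Not all of them would have had SD at the first scan, so this is a ceiling for that component. Resections, new therapy and dropout before the second scan would add a number that cannot be estimated from the documents.

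**The case against.** Several points on the other side stand.

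- SD has to be met only once. A patient who is stable at the first scan and has SD or better at the second is counted. The minimum does not apply to complete or partial response.
- The SAP neither adopts nor waives the minimum. Its best overall response has no SD interval, and the footnotes to its PFS censoring table accept SD as an adequate assessment without one. If the programmer does not apply Attachment 8, nothing is lost.
- Protocol Section 8.4 says that "efficacy measurements are given as targets to be achieved within reasonable limits", so a scan a few days late would be tolerated.
- Rate of resectability is a separate secondary endpoint, so resection itself is not lost from the results.

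Two of these limit the reach of the point without removing it. SAP silence means that two programmers could report different DCRs from the same data. Tolerance of late scans does not reconcile the rules: it makes SD depend on departing from the schedule. The 7-day two-sided window after treatment discontinuation is no dependable rescue either, because it is counted from the baseline scan, which may precede enrollment by up to 28 days.

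A reader might infer that DCR is understated for everyone with SD at the first scan, or that DCR becomes in effect an 11- to 12-week measure. The documents do not support either, for the reasons in the first bullet. Nor is 1 of 32 a probability: it counts date pairs, and nothing says that scan days or lags are equally likely.

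**Conclusion.** The misfit is real and follows from the text. With a lag of 0 to 3 days, a first scan done within its window falls 32 to 42 days after first dose and meets the SD minimum only in an edge case, under either day count and either definition of enrollment.

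The consequence is conditional. If the response algorithm enforces Attachment 8 as written, DCR may be understated by 2.9 points for each patient whose only disease control is SD at the first scan. The documents do not give the number of such patients, and no total should be claimed; the exponential illustration shows only that a handful is plausible.

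The point deserves correction before the final analysis but is not critical. DCR is a descriptive secondary endpoint, SAP Section 5.3.5 says that the study was not designed to assess efficacy, and the primary biomarker objectives, PFS, response rate and resectability are unaffected.

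**What to change.** In Protocol Attachment 8 and SAP Section 5.3.5, state that SD may be assigned at any assessment done within or after the first scheduled on-treatment scan window, that is from 35 days after enrollment, with no separate fixed number of days from first dose. A fixed equivalent such as 32 days would fail whenever the dosing lag exceeds 3 days.

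In the same SAP text, say which enrollment date is the anchor, which day count applies, and how SD seen before the window is classified. Report DCR under the strict rule of 6 weeks from first dose as a sensitivity analysis, so that the effect of the choice is visible.

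The cost is a few sentences and one extra table line. The scan schedule stays as it is. The downside is that SD is credited up to about 42 − 32 = 10 days earlier than under the present wording, or more if the dosing lag is longer than 3 days.

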Attachment 9. Protocol JGDM CYP3A4, CYP2D6, and P-gp Inhibitors and Inducers of Doxorubicin

CYP3A4 Inducers	Strong CYP3A4 Inhibitors	Moderate CYP3A4 Inhibitors
Aminoglutethimide	Clarithromycin	Amiodarone
Bosentan	Chloramphenicol	Amprenavir
Carbamazepine	Cobicistat	Aprepitant ^a
Efavirenz (in liver only)	Conivaptan	Atazanavir
Fosphenytoin	Cremonophor EL	Cimetidine
Nafcillin	Cyclosporine	Ciprofloxacin
Nevirapine	Delavirdine	Clotrimazole
Oxcarbazepine	Diclofenac	Darunavir
Pentobarbital	Diltiazem	Darunavir and ritonavir
Phenobarbital	Elvitegravir and ritonavir	Desipramine
Phenytoin	Enoxacin	Doxycycline
Primidone	Fosamprenavir	Dronedarone
Rifabutin	Grapefruit juice, starfruit, and Seville oranges	Efavirenz
Rifampin	Indinavir	Erythromycin
Rifapentine	Indinavir and ritonavir	FK1706
St. John's wort	Itraconazole	Fluconazole
	Ketoconazole	Fluvoxamine
	Lopinavir and ritonavir	Haloperidol
	Mibefradil	Imatinib
	Miconazole	Metronidazole
	Nefazodone	Norfloxacin
	Nelfinavir	Protease inhibitors
	Nicardipine	Quinidine
	Posaconazole	Schisandra sphenanthera extract
	Quinidine	Sertraline
	Ritonavir	Tetracycline
	Saquinavir	Tofisopam
	Telithromycin	Verapamil
	Theophylline	
	Troleandomycin	
	Voriconazole	

CYP2D6 Inducers	CYP2D6 Inhibitors	P-glycoprotein 1 (P-gp) Inhibitors
Rifampin	Amiodarone	Amiodarone
	Celecoxib	Azithromycin
	Chloroquine	Captopril
	Chlorpromazine	Clarithromycin
	Cimetidine	Cyclosporine
	Citalopram	Piperine
	Clomipramine	Quercetin
	Codeine	Quinidine
	Deiavirdine	Quinine
	Desipramine	Reserpine
	Dextropropoxyphene	Ritonavir
	Diltiazem	Tariquidar
	Doxorubicin	Verapamil
	Entacapone (high dose)	
	Fluoxetine	
	Fluphenazine	
	Fluvoxamine	
	Haloperidol	
	Labetalol	
	Lobeline	
	Lomustine	
	Methadone	
	Mibefradil	
	Moclobemide	
	Nortuloxeline	
	Paroxetine	
	Perphenazine	
	Propafenone	
	Quinacrine	
	Quinidine	
	Ranitidine (ranitidine, Zantac)	
	Risperidone (weak)	
	Ritonavir	
	Serindole	
	Sertraline (weak)	
	Thioridazine	
	Valproic acid	
	Venlafaxine (weak)	
	Vinblastine	
	Vincristine	
	Vinorelbine	
	Yohimbine	

Abbreviation: CYP = cytochrome P450.

- ^a Aprepitant is allowed when given according to local practice and institutional guidelines and if no alternative anti-emetic is recommended.

Attachment 10. Protocol JGDM Protocol Amendment I5B-MC-JGDM(c) Summary: A Phase 1b Trial to Assess the Modulation of Biological Markers in Patients with Potentially Resectable Soft Tissue Sarcoma Treated with Olaratumab Monotherapy Followed by Olaratumab plus Doxorubicin Combination Therapy

Overview

Protocol I5B-MC-JGDM, A Phase 1b Trial to Assess the Modulation of Biological Markers in Patients with Potentially Resectable Soft Tissue Sarcoma Treated with Olaratumab Monotherapy Followed by Olaratumab plus Doxorubicin Combination Therapy, has been amended. The new protocol is indicated by Amendment (c) and will be used to conduct the study in place of any preceding version of the protocol.

The overall changes and rationale for the changes made to this protocol are as follows:

- The term QTcF was defined in the abbreviations and definition section.
- Fridericia's QT correction formula was added for patients with bundle branch block.
- Exclusion criteria 22 was updated by removing language related to the patient's ability to adhere to the protocol and to indicate the exclusion criteria refers to a concomitant systemic disorder the patient is currently experiencing.
- Exclusion criteria 23 was corrected.
- Section 7.1.2. was updated to reference the Pharmacy Manual rather than text from the manual.
- A clarification was made in Section 7.2.3.1 for dose delays that collection of PK samples should be derived from time the actual olaratumab dose was given vs when dose was originally expected.
- Section 8.2.3.2. was corrected for tumor tissue from any posttherapy surgical resection to be optional rather than required.
- Section 10.1. and 10.1.1. was clarified to add the C1D1 predose blood draw to the definition of an evaluable patient.
- A clarification was made in the schedule of events to both treatment and baseline PET scan to move them to the appropriate place in the schedule.
- A change was made in the timing of pre-Dose PK sample in order to allow for samples to be collected before pre-medications are administered.

Revised Protocol Sections

Note: Deletions have been identified by ~~strikethroughs~~.
 Additions have been identified by the use of underscore.
 Where existing language is underlined, additions have been identified by the use of double underscore.

4. Abbreviations and Definitions

QTcF Fridericia's QT corrected interval

